6.7 Efficacy and Effectiveness Assessments

For the closest MRI realized before the initiation of VPRIV® treatment and for each MRI which will be conducted during the prospective one year period, the following information will be recorded whenever they are available in patient's dossiers. Clinical and biological status will also be recorded when treatment was started and the patient included in the study.

- Spine and femur BMB score of T1 and T2 weighted,
- Marrow infiltration, bone infarction, osteonecrosis, pathological fractures (vertebral)

The clinical status:

***Retrospective and prospective observational study of MRI changes in bone and visceral lesions of patients with type 1
Gaucher disease treated with VPRIV® (velaglucerase alfa)***

- Height, weight
- Asthenia (absent / present : mild , moderate or severe), abdominal pain (absent / present : mild , moderate or severe), chronic pain in bone (absent / present : mild , moderate or severe), hemorrhagic syndrome (epistaxis, gingival bleeding, bruising, other rated : absent / present : mild , moderate or severe), lung disease, neurological disease

The biological status:

hemoglobin (g/dl); leukocytes (cells/mm³); platelets (mm³); ACE (angiotensin converting enzyme (U/l); ferritin (mg/l); chitotriosidase (nmol / h / ml); CCL18 (ng/ml), vitamin D (nmol/l), vitamin B12 (pmol/l); SGOT/AST (U/l), SGPT/ALT (U/l), GGT (U/l), alkaline phosphatase (U/l), triglycerides (mmol / l), total cholesterol (mmol/l) gamma globulin (g/l) serum calcium (mmol/l) presence or absence of a monoclonal peak and type if any.

The review will be done on the MRI that the treating physician has addressed for a central review radiological center via the CETG after blinding of the documents.

As previously, the quality of the MRI is evaluated and classified in three categories: Optimal, sub optimal and not assessable according the following definition:

- Optimal: Sufficient anatomical coverage, good image quality with no to minimal image artifacts and compliance with the imaging protocol
- Suboptimal: Sufficient anatomical coverage, presence of moderate image artifacts and/or minor deviations to the imaging protocol, with minimal impact on the analysis
- Not assessable: Insufficient anatomical coverage and/or presence of strong image artifacts and/or severe deviations to the imaging protocol, which would lead to an unreliable analysis.

Spleen/Liver:

TEST	DESCRIPTION	FORMAT/VALUES
ABDO_TECH_AD	Technical Adequacy for Abdominal MRI data	0 = Optimal 1 = Sub optimal 2 = Not assessable
ABDO_TECH_REASON	Reasons for Abdominal MR images not being optimal	List of reasons separated by a
SPLEEN_VOL	Spleen volume (mm3)	FLOAT
LIVER_VOL	Liver Volume (mm3)	FLOAT
SPLEEN_COV	Full Spleen Coverage achieved	Y/N
LIVER_COV	Full Liver Coverage achieved	Y/N
SPLEEN_INF	Presence of Infarcts	Y/N

***Retrospective and prospective observational study of MRI changes in bone and visceral lesions of patients with type 1
Gaucher disease treated with VPRI® (velaglucerase alfa)***

TEST	DESCRIPTION	FORMAT/VALUES
SPLEEN_FD	Presence of Filling Defects	Y/N
LIVER_INF	Presence of Infarcts	Y/N
LIVER_FD	Presence of Filling Defects	Y/N

Spine/Femur:

TEST	DESCRIPTION	FORMAT/VALUES
SPINE_TECH_AD	Technical Adequacy for Spine MR data	0 = Optimal 1 = sub optimal 2 = Not assessable
SPINE_TECH_REASON	Reasons for spine MR images not being optimal	List of reasons separated by a
SPINE_BMB_T1	Spine BMB score of T1-weighted	0 = Slightly hyper intense 1 = Iso intense 2 = Slightly hypo intense 3 = Hypo intense 4 = N/A
SPINE_BMB_T2	Spine BMB score of T2-weighted	0 = Isointense 1 = Slightly hypo intense 2 = Slightly hyper intense 3 = Hypo intense 4 = Hyper intense 5 = N/A
SPINE_BMB_INFILTR	Spine BMB score for Infiltration Pattern	0 = None 1 = Patchy 2 = Diffuse 5 = N/A
SPINE_BMB_FAT	Assessment of Spinal Fat in Basal vertebral Region	3 = Preservation of fat 4 = Absence of fat 5 = N/A
SPINE_COMMENTS	Free Comments on Spine Scoring	
FEMUR_TECH_AD	Technical Adequacy for Femur MR data	0 = Optimal 1 = Readable, but not optimal 2 = Not readable
FEMUR_TECH_REASON	Reasons for Femur MR images not being optimal	List of reasons separated by a
FEMUR_BMB_T1	Femur BMB score of T1-weighted	0 = Slightly hyper intense or isointense 1 = Slightly hypo intense 2 = Hypo intense 3 = N/A
FEMUR_BMB_T2	Femur BMB score of T2-weighted	0 = Isointense 1 = Slightly hypo intense

		2 = Slightly hyper intense 3 = Hypo intense 4 = Hyper intense 5 = Mixed type 6 = N/A
FEMUR_BMB_SITE	Femur BMB score for sites of involvement	0 = No site of involvement 1 = Diaphysis 2 = Proximal epiphysis / apophysis 3 = Distal epiphysis 4 = N/A
FEMUR_COMMENTS	Free comments on femur scoring	

6.8 Safety Assessments

Safety of VPRIV® will be assessed according to ADRs, safety reporting associated with any medication given according to clinical routine. It should also be done according to local applicable drug law and using the procedures of the respective pharmaceutical manufacture.

6.9 Concomitant Medications, Therapies, and Medical/Surgical Interventions Assessments

All medications, therapies/interventions administered to and medical/surgical procedures performed on the study subjects from the time of informed consent through the follow-up contact are regarded as concomitant and will be documented on the CRF.

6.10 Adverse Events Assessments

Definition of Adverse Events/Adverse Drug Reactions, Period of Observation, Recording of Adverse Events/Adverse Drug Reactions

An **Adverse Event** (AE) is any untoward medical occurrence in a clinical investigation patient administered a product and that does not necessarily have a causal relationship with this treatment. An AE can therefore be any unfavorable and unintended sign (including an abnormal laboratory finding), symptom, disease or exacerbation of a pre-existing condition temporally associated with the use of a medicinal product.

Only AEs that will appear only in the prospective part of this observational study and which are considered to be related to Velaglucerase alpha are considered as ADRs, will be collected during this study, ADRs that will be related to the retrospective part of this study will not be collected. (See Section 7.1.2 for further guidance). An ADR is a response to a medicinal product which is noxious and unintended and which occurs at doses normally used in man for prophylaxis, diagnosis, and therapy of disease or for the restoration, correction, or modification of physiological function. Response in this context means that a causal relationship between a medicinal product and an AE is at least a reasonable possibility. Each ADR requires a complete and thorough description on the CRF.

All ADRs, including those associated with the protocol are collected from the time the informed consent is signed until the end of the study duration, are to be recorded on the

appropriate CRF and in source documents. Where possible, a diagnosis rather than a list of symptoms should be recorded. If a diagnosis has not been made then each symptom should be listed individually.

All ADRs (serious and non-serious) must be followed until closure (the patient's health has returned to his/her baseline status or all variables have returned to normal), an outcome is reached, stabilization (the Investigator does not expect any further improvement or worsening of the event), or the event is otherwise explained regardless of whether or not the patient is still participating in the study. When appropriate, medical tests and examinations are performed so that resolution of event(s) can be documented.

Severity Categorisation

The severity of AEs must be recorded during the course of the event including the start and stop dates for each severity. An event that changes in intensity should be captured as a new event. Worsening of pre-treatment events, must be recorded as new AEs (for example if a patient experiences mild intermittent dyspepsia prior to dosing, but the dyspepsia becomes severe and more frequent after first dose of product administration, a new AE of severe dyspepsia (with the appropriate date of onset) is recorded on the appropriate CRF).

The medical assessment of intensity is determined by using the following definitions:

Mild: A type of AE that is usually transient and may require only minimal treatment or therapeutic intervention. The event does not generally interfere with usual activities of daily living.

Moderate: A type of AE that is usually alleviated with specific therapeutic intervention. The event interferes with usual activities of daily living, causing discomfort but poses no significant or permanent risk of harm to the research patient.

Severe: A type of AE that interrupts usual activities of daily living, or significantly affects clinical status, or may require intensive therapeutic intervention.

Relationship Categorisation

An Investigator who is qualified in medicine must make the assessment of relationship to product for each AE. The Investigator should decide whether, in his or her medical judgement, there is a reasonable possibility that the event may have been caused by the product. If there is no valid reason for suggesting a relationship, then the AE should be classified as 'not related'. Otherwise, if there is any valid reason, even if undetermined or untested, for suspecting a possible cause-and-effect relationship between the product and the occurrence of the AE, then the AE should be considered 'related'.

The following additional guidance may be helpful:

***Retrospective and prospective observational study of MRI changes in bone and visceral lesions of patients with type 1
Gaucher disease treated with VPRIV® (velaglucerase alfa)***

Term	Relationship	Definition
Related	Yes	The temporal relationship between the event and the administration of the product is compelling and/or follows a known or suspected response pattern to that product, and the event cannot be explained by the patient's medical condition, other therapies, or accident.
Not Related	No	The event can be readily explained by other factors such as the patient's underlying medical condition, concomitant therapy or accident and no obvious temporal or biologic relationship exists between the product and the event.

Outcome Categorisation

The outcome of AEs must be recorded during the course of the study in the CRF. Outcomes are as follows:

- Fatal
- Not Recovered/Not Resolved
- Recovered/Resolved
- Recovered/Resolved With Sequelae
- Recovering/Resolving
- Unknown

Symptoms of the Disease under Study

Symptoms of the disease under study should not be classed as ADRs as long as they are within the normal day-to-day fluctuation or expected progression of the disease. However, significant worsening of the symptoms should be recorded as an ADR.

Clinical Laboratory Evaluations

A change in the value of a safety laboratory investigation can represent an ADR if the change is clinically relevant or if, during treatment with the product, a shift of a parameter is observed from a normal value to an abnormal value, or a further worsening of an already abnormal value which is assessed to be associated with the use of VPRIV®. When evaluating such changes, the extent of deviation from the reference range, the duration until return to the reference range, either while continuing treatment or after the end of treatment with the product, and the range of variation of the respective parameter within its reference range, must be taken into consideration.

If, at the end of the observation period, there are abnormal laboratory values which were not present at the time of informed consent/patient enrolment, further clinical or laboratory investigations should be

***Retrospective and prospective observational study of MRI changes in bone and visceral lesions of patients with type 1
Gaucher disease treated with VPTRIV® (velaglucerase alfa)***

performed until the values return to within reference range or until a plausible explanation (e.g., concomitant disease) is found for the pathological laboratory values.

The Investigator should decide, based on the above criteria and the clinical condition of a patient, whether a change in a laboratory parameter is clinically significant and therefore represents an AE.

Pregnancy

All pregnancies are to be reported from the time informed consent is signed until the end of the study duration, as applicable.

Any report of pregnancy for any female study participant must be reported within one business day to Shire Pharmacovigilance Department using the Shire Pharmaceuticals Investigational and Marketed Products Pregnancy Form.

Every effort should be made to gather information regarding the pregnancy outcome and condition of the infant. It is the responsibility of the Investigator to obtain this information within 30 calendar days after the initial notification and approximately 30 calendar days post-partum. If no information is received, 1 additional documented follow-up attempt will be made approximately 30 calendar days after the 30-day post-partum contact.

Pregnancy complications such as miscarriage or congenital abnormality are considered SAEs and must be reported using the Shire Pharmaceuticals Clinical Trial Serious Adverse Event Report Form. An elective abortion, which is not associated with any complications, in itself, does not meet the criteria of an SAE.

If the Investigator determines that the pregnancy meets serious criteria, it must be reported as an SAE using the Shire Pharmaceuticals Clinical Trial Serious Adverse Event Report Form. The test date of the first positive serum/UA HCG test or ultrasound result will determine the pregnancy onset date.

Abuse, Misuse, Overdose and Medication Errors

Abuse, misuse, overdose or medication error must be reported to the Sponsor according to the SAE reporting procedure whether or not they result in an AE/SAE as defined in Section 7.2.

- **Abuse** – Persistent or sporadic intentional intake of a product at higher dose than prescribed per protocol (but below the dose defined for overdose) or when used for non-medical purpose (e.g. altering one's state of consciousness).
- **Misuse** – Intentional or un-intentional use of a product other than as directed or indicated at any dose which is at or below the dose defined for overdose (Note: this includes a situation where the test article is not used as directed at the dose prescribed by the protocol).
- **Overdose** – Intentional or un-intentional intake of a dose of a product higher than dosage levels described in the label for VPTRIV®.
- **Medication Error** – A mistake made in prescribing, dispensing, administration, and/or use of the product.

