6.12 Removal of Patients from the Study

A patient's participation in the study may be discontinued at any time at the discretion of the Investigator. The following may be justifiable reasons for the Investigator to remove a patient from the study:

- Non-compliance, including failure to appear at one or more visits (or standard of care)
- The patient was erroneously included in the study
- The patient develops an exclusion criterion
- The patient suffers an intolerable adverse event
- The study is terminated by the Sponsor

The patient, the patient's parent(s), or the patient's legally authorized representative acting on behalf of the patient is free to withdraw consent and discontinue participation in the study at any time without prejudice to further treatment by the physician or at the institution. Discontinued patients should be followed according to medical practice standards.

If a patient or the patient's parent(s) or the patient's legally authorized representative(s) acting on behalf of the patient, discontinues participation in the study, or the patient is discontinued by the Investigator,

***Retrospective and prospective observational study of MRI changes in bone and visceral lesions of patients with type 1
Gaucher disease treated with VPRIV® (velaglucerase alfa)***

reasonable efforts will be made to follow the patient through the end of study assessments. The reason for refusal will be documented on the eCRF. Any adverse events (AE's) experienced up to the point of discontinuation must be documented on the AE eCRF. If AEs are present when the patient withdraws from the study, the patient will be re-evaluated within 30 days of withdrawal. All ongoing SAEs at the time of withdrawal will be followed until resolution.

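### Section 6.10 collects only drug-related events, but its relatedness rules disagree, its disease-worsening rule skips causality, and its scope conflicts with 6.12

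*Protocol*

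**What the plan says.** **Scope.** Protocol section 6.10 limits safety collection to events of the prospective part "which are considered to be related to Velaglucerase alpha are considered as ADRs, will be collected during this study". Section 6.11 defines serious reactions by the same relation to VPRIV.

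**Relatedness, narrative.** The ADR definition in 6.10 asks that "a causal relationship between a medicinal product and an AE is at least a reasonable possibility". Under Relationship Categorisation, an event with no valid reason for a link is not related. Otherwise, "if there is any valid reason, even if undetermined or untested, for suspecting a possible cause-and-effect relationship", it is related.

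**Relatedness, table.** A two-row table follows, introduced as extra guidance that might help. The Related row says: "The temporal relationship between the event and the administration of the product is compelling and/or follows a known or suspected response pattern". It then adds a second condition, "and the event cannot be explained by" the patient's own illness, another treatment or an accident. The Not Related row needs a ready alternative explanation and also that "no obvious temporal or biologic relationship exists between the product and the event".

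**Disease symptoms.** Symptoms within ordinary fluctuation or expected progression are not ADRs, but "significant worsening of the symptoms should be recorded as an ADR".

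**Discontinuation.** Section 6.12 says that any adverse events "experienced up to the point of discontinuation must be documented on the AE eCRF".

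**The concern.** In a study that records all adverse events, a loose causality rule can be repaired later by reclassifying what was recorded. Here relatedness is the entry condition. An event judged unrelated is outside the collection rule, and a serious one is also outside the one-business-day reporting in 6.11. Two relatedness standards in the same section therefore mean that the recorded set depends on which sentence an investigator follows.

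The other two conflicts act on the same data. A disease event recorded as an ADR by default is called a drug reaction without anyone having judged it so. A wider rule at discontinuation means that unrelated events may be recorded for some patients and not for others.

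What is at stake is the safety description. Section 4.10 gives safety in real-life conditions as part of the design rationale, section 6.8 assesses safety through ADRs, and section 8.5 plans MedDRA coding and description of events.

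**Working it through.** There is no stated figure to reproduce, so the check sets the rules side by side.

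**1. Narrative against table.** Events are sorted by the strength of the drug link and by whether another cause readily explains them. A strong link means compelling timing or a known or suspected response pattern.

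| Drug link | Other explanation | Narrative | Table |
|---|---|---|---|
| Strong | No | Related | Related |
| Strong | Yes | Related | Neither row |
| Weaker, but a valid reason | No | Related | Neither row |
| Weaker, but a valid reason | Yes | Related | Not related if the link is not obvious, otherwise neither row |
| None | Yes | Not related | Not related |
| None | No | Not related | Neither row |

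The narrative places every event in exactly one category. The table agrees with it in 2 of the 6 combinations. In three of the other four, the narrative calls the event related and the Related row does not. These are combinations, not frequencies, and say nothing about how often each occurs.

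Nothing in the protocol settles which rule prevails. Section 6.10 points to a section 7.1.2 for further guidance on collection, but section 7.1 concerns the appropriateness of the MRI measurements and has no such subsection.

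**2. ADR definition against the disease-symptom rule.** The definition in 6.10 requires at least a reasonable possibility of causation. The disease-symptom sentence goes from significant worsening straight to an ADR. A worsening with no suspected drug link is not an ADR under the definition but is one under that sentence.

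**3. ADR-only scope against the other collection rules.**
- Section 6.12 requires any adverse event up to discontinuation, with no relatedness condition.
- Section 6.10 (Severity Categorisation) requires worsening of pre-treatment events to be recorded as new adverse events, not as ADRs.
- Section 6.10 (Outcome Categorisation) requires the outcome of adverse events to be recorded in the CRF.

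Each presupposes that events are recorded whether related or not.

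**4. Scale.** Section 8.2 expects 40 to 50 patients. Moving one patient into or out of the count for a given reaction changes its incidence by 1/50 = 2.0 to 1/40 = 2.5 percentage points. This shows the weight of one patient. It is not an estimate of how many events are affected.

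**The case against.** The strongest reply is that the table is optional. The narrative obliges the investigator to assess every event, is exhaustive, and matches the ADR definition. An event that the table leaves unclassified can fall back to the narrative, which calls it related. This largely stands as a reading of intent. It does not remove the defect: no precedence is stated, and guidance that contradicts the rule it is meant to explain invites the wrong decision.

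A second reply is that safeguards exist. Section 6.11 encourages discussion of ADRs of unclear relationship with the medical monitor, section 7.1 plans training and manuals, and section 9.9 guarantees access to source documents. These help, and events left out are not necessarily beyond recovery. But the discussion is voluntary and concerns events already treated as ADRs, and the protocol plans no systematic search of records for events left out.

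Four stronger readings are tempting and not supported:
- **That the table loses a definable share of reactions.** Unclassified is not the same as excluded. Loss needs an investigator to treat the Related row as a requirement, and the protocol gives no basis for a percentage.
- **That ordinary Gaucher progression is counted as a drug reaction.** Expected progression is expressly excluded; only significant worsening beyond it is affected. The general duty to assess each event can be read into that sentence, but the sentence does not say so.
- **That 6.12 supplies another definition of relatedness.** It concerns which events are recorded. Nor is the wider wording confined to patients who leave, since 6.10 itself speaks of recording adverse events in general.
- **That a planned comparison is biased.** The protocol plans no safety comparison between sites, or between withdrawn and remaining patients, and safety is not among the objectives in section 2 or the endpoints in section 3.

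**Conclusion.** Wrong as written. The protocol makes relatedness the condition for recording an event and then gives rules on relatedness and scope that cannot all be followed. Following the text literally can produce misclassified or unevenly collected safety data.

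The three parts differ in weight. The table conflict matters only where an investigator lets the table override the narrative. The disease-worsening rule contradicts the ADR definition on its face. The scope conflict between ADR-only collection and 6.12 is a separate defect and holds whichever relatedness rule is used.

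The size cannot be calculated: the protocol does not give the number of suspected reactions, the share with another possible cause, or the number of discontinuations. The effect is limited to the safety description. The BMB primary endpoint and the other MRI analyses are untouched.

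**What to change.** Reconcile the passages in three places.

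1. **Relationship table (6.10).** Reword it to match the narrative rule so that every event falls in exactly one row, and state that the narrative governs. Correct or remove the pointer to section 7.1.2.
2. **Disease symptoms (6.10).** Make significant worsening beyond expected progression an ADR only after the same causality assessment as any other event.
3. **Scope (6.10 and 6.12).** State once whether all adverse events or only ADRs are recorded, apply it equally to patients who stay and patients who leave, and bring the wording on pre-treatment events and outcomes into line. Either scope would remove the contradiction.

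The cost is minor wording in two sections and matching CRF completion guidance, with the approval that section 9.7 requires for protocol modifications. A few more events may be recorded. No MRI procedure or efficacy analysis changes.
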